8.1.1. Adverse Event Dictionary

Clinical and laboratory adverse events (AEs) will be coded using the current version of MedDRA. System organ class (SOC), high-level group term (HLGT), high-level term (HLT), preferred term (PT), and lower-level term (LLT) will be provided in the AE dataset.

8.1.2. Adverse Event Severity

Adverse events are graded by the investigator as Grade 1, 2, 3, 4, or 5 according to Common Terminology Criteria for Adverse Events (CTCAE) Grading Scale. If CTCAE criteria do not exist for a specific event, [Table 7-1](#) of the study protocol provides guidance for the investigator to grade the event. The severity grade of events for which the investigator did not record severity will be categorized as “missing” for tabular summaries and data listings. The missing category will be listed last in summary presentation.

8.1.3. Relationship of Adverse Events to Study Drug

Related AEs are those for which the investigator selected “Related” on the AE eCRF to the question of “Related to Study Treatment.” Relatedness will always default to the investigator’s choice, not that of the medical monitor. Events for which the investigator did not record relationship to study drug will be considered related to study drug for summary purposes. However, by-subject data listings will show the relationship as missing.

8.1.4. Serious Adverse Events

Serious adverse events (SAEs) will be identified and captured as SAEs if the AEs met the definitions of SAEs that were specified in the study protocol. SAEs captured and stored in the clinical database will be reconciled with the SAE database from the Gilead Global Patient Safety (formerly Gilead Pharmacovigilance and Epidemiology) Department before database finalization.

8.1.5. Treatment-Emergent Adverse Events

8.1.5.1. Definition of Treatment-Emergent Adverse Events

Treatment-emergent adverse events (TEAEs) are defined as 1 or both of the following:

- Any AEs with an onset date on or after the study drug start date and no later than 30 days after permanent discontinuation of study drug
- Any AEs leading to premature discontinuation of study drug

In “as-treated” displays, subjects who took double-blind placebo and switched to open-label filgotinib with TEAEs with an onset date on/after first dose date of double-blind placebo and prior to the first dose date of open-label filgotinib will be attributed to the placebo period (and summarized with the placebo treatment group). TEAEs with an onset date on or after the first dose date of open-label filgotinib up to last dose date of open-label filgotinib + 30 days or AEs that led to premature discontinuation of OL filgotinib will be attributed to the filgotinib period (and summarized with the filgotinib treatment group).

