7.2.2. Assessment of Severity

The severity of AEs will be graded using the modified Common Terminology Criteria for Adverse Event (CTCAE), version 4.03. For each episode, the highest grade attained should be reported.

If a CTCAE criterion does not exist, the investigator should use the grade or adjectives: Grade 1 (mild), Grade 2 (moderate), Grade 3 (severe), Grade 4 (life-threatening) or Grade 5 (fatal) to describe the maximum intensity of the adverse event. For purposes of consistency with the CTCAE, these intensity grades are defined in [Table 7-1](#) and [Appendix 4](#).

Table 7-1. Grading of Adverse Event Severity

Grade	Adjective	Description
Grade 1	Mild	Asymptomatic or mild symptoms; clinical or diagnostic observations only; intervention not indicated
Grade 2	Moderate	Local or noninvasive intervention indicated; limiting age-appropriate instrumental ADL*
Grade 3	Severe	Severe or medically significant but not immediately life-threatening; hospitalization or prolongation of hospitalization indicated; disabling; limiting self-care ADL**
Grade 4	Life-threatening	Urgent intervention indicated
Grade 5	Death	Death-related AE

* Activities of Daily Living (ADL) Instrumental ADL refer to opening preparing meals, shopping for groceries or clothes, using the telephone, managing money, etc.

** Self-care ADL refer to bathing, dressing and undressing, feeding self, using the toilet, taking medications, and not bedridden.

7.3. Investigator Requirements and Instructions for Reporting Adverse Events and Serious Adverse Events to the Sponsor

Requirements for collection prior to study drug initiation:

After informed consent, but prior to initiation of study drug, the following types of events should be reported on the case report form (CRF/eCRF): all SAEs and adverse events related to protocol-mandated procedures.

Adverse Events

Following initiation of study drug, collect all AEs, regardless of cause or relationship, until 30-days after last administration of study drug(s) must be reported to the CRF/eCRF database as instructed.

All AEs should be followed up until resolution or until the adverse event is stable, if possible. The Sponsor may request that certain AEs be followed beyond the protocol defined follow up period.

Serious Adverse Events

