8.1. Adverse Events and Deaths

Up to 3 different displays of adverse event data may be presented as described in Section 3.2 of this SAP:

“As-treated” analysis: Subjects who switched from placebo to open-label filgotinib will have adverse events occurring while on double-blind study drug summarized with placebo, and adverse events occurring on/after first dose date of open-label filgotinib to last dose date of filgotinib plus 30 days (if permanently discontinued), or all available data if ongoing at time of an interim analysis summarized with filgotinib. All other subjects will have adverse events occurring on/after first dose date of any study drug to last dose date of any drug plus 30 days (if permanently discontinued), or all available data if ongoing at time of interim analysis summarized by treatment received. This analysis will summarize all on-treatment adverse events and will be used to scan for all safety events during the study.

During Double-Blind Phase of the Study: Data will be included up to first dose date of open-label filgotinib minus 1 day for subjects who switched to open-label filgotinib; last dose date of double-blind study drug plus 30 days for those who have permanently discontinued from study drug; or all available data while on double-blind drug if ongoing at the time of an interim analysis. This analysis will summarize adverse events during the same timeframe as the primary analysis for sperm/semen data.

During Open-Label Filgotinib Phase of the Study: Data will be included from OL Day 1 to last dose date of open-label filgotinib plus 30 days for those who have permanently discontinued from open-label filgotinib; or all available data if ongoing at the time of an interim analysis. These displays will summarize data for subjects in the Open-Label Filgotinib Safety Analysis Set. This analysis appropriately adjusts the denominator for interruptions and discontinuations for open-label filgotinib to only those subjects who took open-label filgotinib.

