- All TEAEs by Concomitant Medication Use (Immunomodulator and Corticosteroid Use)
- TEAEs of Grade 3 or higher (by maximum severity)

- TEAEs of Grade 2 or higher
- TE treatment-related AEs
- TE Treatment-related AEs of Grade 3 or higher (by maximum severity)
- TE SAEs
- TE SAEs by Concomitant Medication Use (Immunomodulator and Corticosteroid Use)
- TE treatment-related SAEs
- TEAEs leading to premature discontinuation of study
- TEAEs leading to death

Multiple events will be counted only once per subject in each summary. Adverse events will be summarized and listed first in alphabetic order of SOC and HLT within each SOC (if applicable), and then by PT in descending order of total frequency within each SOC. For summaries by severity grade, the most severe grade will be used for those AEs that occurred more than once in an individual subject during the study.

In addition to the above summary tables, all TEAEs, SAEs, and TE treatment-related AEs will be summarized (for the double-blind phase and for “as-treated” analysis) by PT only, in descending order of total frequency.

In addition, data listings will be provided for the following:

- All AEs, indicating whether the event is treatment emergent
- All AEs of Grade 3 or higher
- SAEs
- Deaths
- COVID-19 Adverse Events
- All AEs leading to temporary interruption of double-blind study drug
- All AEs leading to temporary interruption of open-label filgotinib study drug
- AEs leading to premature discontinuation of double-blind study drug
- AEs leading to premature discontinuation of open-label filgotinib study drug

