8.2.2.1. Treatment-Emergent Laboratory Abnormalities

Treatment-emergent laboratory abnormalities are defined as values that increase at least 1 toxicity grade from baseline at any postbaseline time point, up to and including the date of last dose of any study drug plus 30 days for subjects who permanently discontinued study drug, or the last available date in the database snapshot for subjects who were still on treatment at the time of an interim analysis.

For “as-treated” displays and subjects who took double-blind placebo and switched to open-label filgotinib, treatment-emergent laboratory abnormalities for the placebo period (summarized with placebo group) are defined as values that increase at least 1 toxicity grade from baseline at any postbaseline time point, up to and including the first dose date of open-label filgotinib. Treatment-emergent laboratory abnormalities of the filgotinib period (summarized with filgotinib group) are defined as values that increase at least 1 toxicity grade from the Open-label Baseline up to and including the date of last dose of any study drug plus 30 days, or the last available date in the database snapshot for subjects who were still on treatment at the time of an interim analysis.

For all other subjects, treatment-emergent laboratory abnormalities are defined as values that increase 1 toxicity grade from the double-blind baseline at any postbaseline time point, up to and including the date of last dose of any study drug plus 30 days (or all available data if ongoing at an interim analysis).

If the relevant baseline laboratory value is missing, any abnormality of at least Grade 1 observed within the time frame specified above will be considered treatment emergent.

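### In the as-treated tables, an adverse event that starts on placebo and turns severe or serious on open-label filgotinib, without ending that treatment, is shown as a placebo event only

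*SAP*

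**What the plan says.** **Assignment to a period.** In the as-treated displays (SAP 8.1.5.1), a placebo man who later switches has his treatment-emergent events placed by onset. Those starting on or after his first placebo dose and "prior to the first dose date of open-label filgotinib will be attributed to the placebo period". Those starting from the first open-label dose onward belong to filgotinib. One exception follows directly: "AEs that led to premature discontinuation of OL filgotinib will be attributed to the filgotinib period".

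**Grade and seriousness.** Protocol 7.2.2: "For each episode, the highest grade attained should be reported". SAP 8.1.4 treats seriousness as a property of the event: "Serious adverse events (SAEs) will be identified and captured as SAEs if the AEs met the definitions of SAEs". It does not ask when the event became serious.

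**Counting.** SAP 8.1.6: "Multiple events will be counted only once per subject in each summary". In summaries by severity, "the most severe grade will be used for those AEs that occurred more than once in an individual subject during the study".

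**Double-blind display.** SAP 8.1, for men who switch: "Data will be included up to first dose date of open-label filgotinib minus 1 day".

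**Laboratory data.** For the same switchers, SAP 8.2.2.1 defines filgotinib-period abnormalities as "values that increase at least 1 toxicity grade from the Open-label Baseline". SAP 8.2.2.2 does the same for marked abnormalities.

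**Other rules that send events to filgotinib.** In the brief summary of SAP 8.1.6, a death in a man who took any open-label dose is shown with open-label filgotinib. Under SAP 8.1.5.2, an event goes to filgotinib if its onset date is missing, or is incomplete and falls in the month of the switch, and its stop date is missing or not before the first open-label dose.

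**The concern.** The period is fixed by when the episode began, but the grade and seriousness shown are those of the whole episode. Protocol 7.3 follows adverse events until they resolve or stabilise, so an episode open at the switch is still observed, and can still worsen, on filgotinib. No rule splits the episode at the switch or limits its grade to the period of onset.

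The tables at stake are the as-treated summaries of Grade 3 or higher events and of SAEs. SAP 8.1 says that this analysis serves to scan for all safety events in the study. In these displays, men randomized to filgotinib who move to open-label drug stay in the filgotinib column (SAP 3.2), so their crossing episodes do not balance those of the placebo switchers. In a safety study, a rule that moves severe events from the test drug to placebo errs in the wrong direction.

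**Working it through.** The documents state no figure on this point, so there is none to reproduce. The check applies the written rules to test episodes and then scales one affected man.

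**Step 1. Rules applied.** Take a placebo man whose open-label treatment starts on Day 106 (hypothetical days).

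| Episode | By onset | By discontinuation exception | Where shown |
|---|---|---|---|
| A: Grade 1 on Day 90; Grade 3 and serious on Day 120; drug continued | placebo | not triggered | Grade 3 SAE, placebo only |
| B: as A, but open-label drug stopped because of it | placebo | filgotinib | both sentences apply; no precedence stated |
| C: new onset at Grade 3 on Day 120 | filgotinib | not triggered | Grade 3, filgotinib |

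Episode A is the defect. Episode B is an ambiguity. Episode C is handled correctly.

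**Step 2. Contrast with laboratory data.** If the same man's laboratory grade rose from 1 at the Open-label Baseline to 3 on Day 120, SAP 8.2.2.1 would count it under filgotinib. The same course recorded as an adverse event is counted under placebo.

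**Step 3. Double-blind display.** Events enter by onset before the switch, again with no limit on the grade. This applies to switchers from both arms, so the direction of any net effect depends on how many men in each arm carry an open event across the switch.

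**Step 4. Weight of one type-A man (illustration).** Inputs:
- n = 125 per arm, the planned maximum in Protocol 8.7.
- s = 25 to 100 placebo switchers. This is an assumption; the documents do not give the number.
- The as-treated filgotinib column has n + s men, because SAP 3.1.3 adds the switchers to it.
- The man has no other Grade 3 or higher or serious event in either period.

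Excess in the placebo percentage = 100/n = 100/125 = 0.80 points.

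Deficit in the filgotinib percentage = 100/(n + s): 100/150 = 0.67 points at s = 25, and 100/225 = 0.44 points at s = 100.

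Shift in the filgotinib-minus-placebo difference = sum of the two: 0.80 + 0.67 = 1.47 points at s = 25, and 0.80 + 0.44 = 1.24 points at s = 100, in favour of filgotinib.

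Protocol 8.7 plans about 250 men over this study and the rheumatic-disease study together, so the arms here may be smaller than 125. Each man would then weigh more.

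**The case against.** **Many of the worst cases already go to filgotinib.** Protocol 3.3.2 requires permanent discontinuation for, among others, opportunistic infections, infections meeting SAE criteria and thromboembolic SAEs. Protocol 7.6.3 adds confirmed, related Grade 4 events. The discontinuation exception then applies. Deaths in the brief summary and some incompletely dated events also go to filgotinib. This stands, and it limits the effect to worsening that did not end open-label treatment.

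**A worsening may be recorded as a new event.** The eCRF completion guidelines, which are not among the documents, could require this. Protocol 7.1.1 does count pre-existing events that worsen as adverse events, but in context that concerns conditions present before participation. The plan as written has no such rule at the switch.

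**The tables are descriptive.** The planned between-arm difference for adverse events is the exposure-adjusted rate difference for events of interest in the double-blind phase (SAP 8.1.7). Listings of adverse events and SAEs are also planned, so a careful reader could find crossing episodes. This lowers the stakes but does not correct the tables.

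**Onset-based assignment is conventional.** Some worsening after the switch will be the natural course of disease in placebo non-responders. That is fair, and it is why the remedy is a second display rather than a replacement.

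**Stronger readings that a reader might infer.** One is that the worst-grade rule for repeated events is a second route by which open-label grades reach the placebo column. A recurrence that starts on open-label drug is itself a filgotinib event, and the tables are limited by period. The phrase *during the study* would have to be read across periods, and it would then also carry placebo grades into the filgotinib column. Another is that the error can only favour filgotinib. That holds for crossing episodes in the as-treated display. It does not hold for the double-blind display, nor for the rules on deaths and incomplete dates.

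**Conclusion.** The point holds for one defined group: placebo men with an episode open at the first open-label dose that becomes Grade 3 or higher, or serious, afterwards without ending open-label treatment. In the as-treated tables these are shown as severe or serious placebo events and are missing from filgotinib, so for them the bias favours filgotinib. In the double-blind display the grade is equally unlimited, but in both arms.

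The total size cannot be derived. The documents give neither the number of switchers, nor how many had an open event, nor how many of those worsened. The Phase 2 Crohn's disease placebo response in Protocol 1.3.2 is a poor guide to the switch rate, because SAP 6.7 says that only a few Crohn's subjects were enrolled. What can be said is the weight per man: about 1.2 to 1.5 points on the difference, under the assumed 125 per arm and 25 to 100 switchers. A claim that the comparison is off by several points would need event counts that are not available. This is a worthwhile, inexpensive improvement to safety tables. It does not touch the primary semen analysis.

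**What to change.** 1. **Second display.** Show the as-treated Grade 3 or higher TEAE and SAE tables a second time. Count under filgotinib any event that began on placebo, was ongoing at the first open-label dose and is recorded as Grade 3 or higher or serious, unless the record shows that this grade or seriousness was reached before that dose. Where the date of worsening is available or can be queried, assign by that date, in line with SAP 8.2.2.1.
2. **Precedence.** State in SAP 8.1.5.1 which sentence prevails when a placebo-onset event leads to discontinuation of open-label filgotinib.
3. **Clarification only.** In SAP 8.1.6, replace *during the study* in the worst-grade rule with *within the treatment period displayed*.

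**Cost.** The second display needs only onset, stop and dose dates plus the recorded grade and seriousness, so it takes a little programming and some wording. Queries on dates of worsening are optional and confined to events open at the switch. SAP 1 allows changes after finalization if they are documented in the CSR, so the final analysis can adopt this.

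**Downside.** A few events will appear under both treatments across the displays, and some natural disease worsening in placebo non-responders will be counted under filgotinib in the second one. A footnote should say so.

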8.1.5.2. Incomplete Dates

If the onset date of the AE is incomplete and the AE stop date is not prior to the first dosing date of study drug, then the month and year (or year alone if month is not recorded) of onset determine whether an AE is treatment emergent. The event is considered treatment emergent if both of the following 2 criteria are met:

- The AE onset is the same as or after the month and year (or year) of the first dosing date of study drug, and
- The AE onset date is the same as or before the month and year (or year) of the date corresponding to 30 days after the date of the last dose of study drug

An AE with completely missing onset and stop dates, or with the onset date missing and a stop date later than the first dosing date of study drug, will be considered to be treatment emergent. In addition, an AE with the onset date missing and incomplete stop date with the same or later month and year (or year alone if month is not recorded) as the first dosing date of study drug will be considered treatment emergent.

For “as-treated” displays, subjects who took double-blind placebo and switched to open-label filgotinib, reporting an AE with incomplete onset date that is prior to the month and year (or year) of the first dose date of open-label filgotinib will have that AE attributed to the placebo period (and summarized with the placebo treatment group). An AE with incomplete onset date that is in the same or after the month and year (or year) of the first dose date of open-label filgotinib up to last dose date of open-label filgotinib + 30 days will be attributed to the filgotinib period (and summarized with the filgotinib treatment group).

In addition, an AE with completely missing onset date or incomplete onset date that is same as the month and year (or year) of the first dose date of open-label filgotinib, and stop date that is prior to the date (or month and year if day is not recorded; or year alone if month is not recorded) of the first dose of open-label filgotinib will be attributed to the placebo period (and summarized with the placebo treatment group). An AE with completely missing onset date or incomplete onset date that is same as the month and year (or year) of the first dose date of open-label filgotinib, and stop date that is missing, or the same as, or after the date (or month and year if day is not recorded; or year alone if month is not recorded) of the first dose of open-label filgotinib up to last dose date of open-label filgotinib + 30 days will be attributed to the filgotinib period (and summarized with the filgotinib treatment group).

8.1.5.3. Analysis of Exposure-Adjusted Incidence Rates

The Exposure-Adjusted Incidence Rate (EAIR) is defined as:

$$\begin{aligned} & \text{Incidence rate per 100 patient years of exposure (PYE)} \\ & = \frac{\text{Total number of subjects with an event}}{\text{Total PYE}} \times 100. \end{aligned}$$

The total patient-years of exposure (PYE) to a treatment is the sum of the individual subject's PYE, which is defined as:

- For subjects with an event:

$$PYE = (Event\ start\ date - first\ dosing\ date + 1) / 365.25.$$

When calculating PYE, a partial AE onset date will be imputed as follows:

- If the non-missing portion of the AE onset date (month and/or year) is the same as the portion of the first dosing date (month and/or year) of start of study drug, the AE onset date will be imputed as the first dosing date of study drug; otherwise it will be imputed as the 1st day of month (if only day is missing) or January 1st of the year (if day and month are missing).
 - If the AE onset date is completely missing, the AE onset date will be imputed as the first dosing date of study drug.
- For subjects with no event:

$$PYE = (Calculation\ end\ date - first\ dosing\ date + 1) / 365.25,$$

For double-blind phase:

First dosing date = double-blind first dose date

Calculation end date = earliest non-missing date of (last dosing date of double-blind drug + 30, first dosing date of OL filgotinib (if applicable) – 1, data cutoff date, death date)

For as-treated analysis:

Filgotinib exposure for Placebo to OL filgotinib: first dosing date = first dose date OL filgotinib; calculation end date is earliest non-missing date among (last dose date of OL filgotinib + 30 days, data cutoff date, death date)

Placebo exposure for Placebo to OL filgotinib: first dosing date = first dose date placebo; calculation end day is earliest non-missing date among (first dose date OL filgotinib – 1, data cutoff date, death date).

Exposure for subjects remaining on double-blind drug: first dosing date = first dose date double-blind drug; calculation end date is earliest date among (last dose date double-blind drug + 30, data cutoff date, death date)

Filgotinib exposure for Filgotinib to OL filgotinib: first dosing date = first dose date double-blind drug; calculation end day is earliest non-missing date among (last dose date of open-label filgotinib + 30, data cutoff date, death date).

The exact 95% CI based on Poisson distribution {Ulm 1990} for EAIR is defined as:

$$\left(\frac{\chi^2_{2(\text{Total number of subjects with an event}),0.025}}{2 \times \text{Total PYE}}, \frac{\chi^2_{2(1+\text{Total number of subjects with an event}),0.975}}{2 \times \text{Total PYE}} \right) \times 100.$$

Partial last dosing dates of double-blind phase will be imputed as described in section 4.2.1.

In addition to by treatment group summary, the EAIR difference with 95% CI for filgotinib minus placebo will be presented. The Method of Variance Estimates Recovery (MOVER)-type confidence interval described in {Li 2011} will be used to calculate EAIR difference and 95% CI:

$$L = \frac{n_a}{T_a} - \frac{n_b}{T_b} - \sqrt{\left(\frac{n_a}{T_a} - l_a\right)^2 + \left(u_b - \frac{n_b}{T_b}\right)^2}, \quad U = \frac{n_a}{T_a} - \frac{n_b}{T_b} + \sqrt{\left(u_a - \frac{n_a}{T_a}\right)^2 + \left(\frac{n_b}{T_b} - l_b\right)^2},$$

where n_a is the total number of subjects with the event, T_a is the total PYE, l_a is the lower bound and u_a is the upper bound of the exact 95% CI based on Poisson distribution for group a .

Similarly for group b .

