8.1.7. Adverse Events of Interest

Adverse events of interest (AEIs) include infections, gastrointestinal perforations, herpes zoster, malignancies (excluding non-melanoma skin cancers), non-melanoma skin cancers, and thromboembolic events. Summaries of the following treatment-emergent AEIs will be produced to enhance the analysis of safety data.

- Events of infection presented in the following subcategories:
 - AEs of infections, utilizing all AEs in the MedDRA Infections and Infestations SOC
 - AEs of serious infections, using all AEs in the MedDRA Infections and Infestations SOC that are classified as SAEs
 - AEs of herpes zoster, utilizing a MedDRA search term (MST) list developed by Gilead
 - AEs of opportunistic infections (OIs), using a Standardized MedDRA Query (SMQ)--narrow scope
 - Active tuberculosis, using an MST list developed by Gilead
 - Hepatitis B or C infections, using an MST list developed by Gilead
- AEs of malignancies, excluding non-melanoma skin cancers, utilizing a MST list developed by Gilead
- AEs of non-melanoma skin cancers, utilizing a MST list developed by Gilead
- AEs of gastrointestinal perforation, utilizing a MST list developed by Gilead
- AEs of arterial or venous thrombosis and/or thromboembolism, presented in the following subcategories:
 - AEs of venous thrombosis, utilizing a MST list developed by Gilead
 - AEs of pulmonary embolism, utilizing a MST list developed by Gilead
 - AEs of arterial thrombosis, utilizing the embolic and thrombotic events, arterial Standardised MedDRA Queries (SMQ)
 - AEs of cerebrovascular events, utilizing the ischaemic central nervous system vascular conditions SMQ

For the double-blind phase, the number of subjects with a TE AEI (and SAE), the corresponding PYE, the calculated EAIR, and the exact 95% CIs (defined in Section 8.1.5.3) will be summarized for each treatment group by PT. The EAIR difference (filgotinib – placebo) and corresponding 95% CIs for the difference between treatment groups will also be presented for the double-blind phase of the study.

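### SAP 8.1.5.3: the confidence limits for the adverse-event rate difference combine rates per 1 patient-year with Poisson limits per 100 patient-years, so the formula as written is wrong

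*SAP*

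**What the plan says.** SAP 8.1.5.3 builds the comparison in three steps.

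1. The EAIR is the number of subjects with an event divided by total PYE, times 100.
2. An exact Poisson interval "for EAIR is defined as" chi-square quantiles divided by twice the total PYE, with both limits multiplied by 100.
3. For the comparison, "the EAIR difference with 95% CI for filgotinib minus placebo will be presented", using a MOVER-type interval. Its limits L and U are built from n_a/T_a and n_b/T_b with no factor of 100. The definitions under the formula say that "T_a is the total PYE", and that u_a "is the upper bound of the exact 95% CI based on Poisson distribution for group" a; l_a is the matching lower bound, and group b is treated likewise.

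SAP 8.1.7 applies this to adverse events of interest and SAEs in the double-blind phase: "The EAIR difference (filgotinib – placebo) and corresponding 95% CIs for the difference between treatment groups will also be presented". The same section also requires, for each arm, the event count, PYE, EAIR and exact interval.

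**The concern.** The MOVER method combines each estimate with its own confidence limits: every squared term is the distance from a rate to its limit. Here the rate is per 1 PYE, but the only Poisson interval that the SAP defines is per 100 PYE. Each squared term therefore becomes close to the whole limit instead of that distance. The point difference also comes out per 1 PYE, next to group rates per 100 PYE.

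This is the only between-arm interval for adverse events in the readable SAP; the other summaries are counts, percentages or single-arm rates. It covers infections, serious infections, herpes zoster, malignancy and thromboembolic events. Protocol 1.4 expects JAK inhibition to raise infection risk, so this comparison should be able to show a difference if there is one.

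**Working it through.** The SAP gives no worked EAIR, so there is no stated figure to reproduce.

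**Inputs.** The formulas are those of SAP 8.1.5.3. Exposure of 50 PYE per arm is an assumption (100 men at 0.5 year each), and the event counts are assumptions too. With equal exposure in both arms the width ratio does not depend on the PYE chosen.

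**Formulas.** l = chi2(0.025; 2n)/(2T), taken as 0 when n = 0, and u = chi2(0.975; 2(n+1))/(2T), before any multiplication by 100. With a = n_a/T_a and b = n_b/T_b:

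- L = a - b - sqrt[(a - l_a)² + (u_b - b)²]
- U = a - b + sqrt[(u_a - a)² + (b - l_b)²]

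**One case in full: 6 v 0, T = 50.** a = 0.12, l_a = 0.0440, u_a = 0.2612, b = 0, l_b = 0, u_b = 0.0738.

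- *One scale.* L = 0.12 - sqrt(0.0760² + 0.0738²) = 0.12 - 0.1059 = 0.0141. U = 0.12 + 0.1412 = 0.2612. Times 100: difference 12.0, interval 1.4 to 26.1.
- *As written* (limits times 100, rates not). L = 0.12 - sqrt((0.12 - 4.40)² + 7.38²) = 0.12 - 8.53 = -8.4. U = 0.12 + (26.12 - 0.12) = 26.1. Difference 0.12, interval -8.4 to 26.1.

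**Other counts, 50 PYE per arm.** The width ratio reads the as-written limits as per 100 PYE.

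| Filgotinib v placebo | One scale, per 100 PYE | As written | Width ratio |
|---|---|---|---|
| 0 v 0 | 0.0 (-7.4, 7.4) | 0.00 (-7.4, 7.4) | 1.00 |
| 3 v 0 | 6.0 (-2.8, 17.5) | 0.06 (-7.4, 17.5) | 1.23 |
| 5 v 2 | 6.0 (-6.4, 19.8) | 0.06 (-14.7, 23.3) | 1.45 |
| 6 v 0 | 12.0 (1.4, 26.1) | 0.12 (-8.4, 26.1) | 1.40 |
| 10 v 8 | 4.0 (-14.7, 23.1) | 0.04 (-32.7, 37.2) | 1.85 |
| 15 v 3 | 24.0 (6.5, 44.1) | 0.24 (-23.8, 49.4) | 1.95 |
| 20 v 5 | 30.0 (9.5, 52.8) | 0.30 (-33.1, 61.8) | 2.19 |
| 30 v 10 | 40.0 (14.3, 67.7) | 0.40 (-53.7, 86.0) | 2.61 |
| 40 v 20 | 40.0 (8.4, 72.9) | 0.40 (-82.9, 111.2) | 3.01 |

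If the as-written limits are instead read on the scale of the as-written point difference, per 1 PYE, each ratio is 100 times larger.

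**Why the as-written interval cannot exclude zero.** L > 0 needs a - b > 100u_b - b, that is, n_a/T_a > 100u_b. The smallest possible u_b, with no placebo events, is 3.69/T_b, so 100u_b is at least 369/T_b. With T_a = T_b this requires more than 369 filgotinib subjects with the event. Protocol 8.7 plans at most 125 per arm. By symmetry U cannot fall below zero. A numerical grid agrees (0 to 80 events per arm, equal PYE of 25 to 200 per arm): the one-scale lower limit is above zero in 10,225 of 32,805 cases, the as-written one in none.

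**The case against.** The strongest reply is that this is a notation gap. Inside a term such as n_a/T_a minus l_a, the only coherent meaning of l_a is the Poisson limit for n_a/T_a, and the named method pairs each estimate with its own limits. A programmer who knows the method would get the right interval. It stands that the documents do not show the program, which may be correct. But the unscaled interval is defined nowhere in the SAP, and the two methodological sources cited for these formulas are missing from its reference list (Section 10), so the text does not settle the scale.

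Three further points carry weight.

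- **Small counts.** Results are tabulated by preferred term, so many counts will be low. At 50 PYE per arm the correct interval already includes zero for 3 v 0, 5 v 1 and 7 v 1. The conclusion changes only from about 6 v 0 or 8 v 1 upward.
- **Other columns in the display.** The per-arm rates and exact intervals are on one scale and correct. For 20 v 5 they are 40.0 (24.4 to 61.8) and 10.0 (3.2 to 23.3), which do not overlap. A difference of 0.30 beside those rates would be conspicuous.
- **Exposure.** Double-blind PYE under the SAP stops at event onset, can run to 30 days after the last blinded dose, and includes blinded long-term extension time. The 50 PYE is therefore only illustrative, and the arms may differ. With unequal exposure the necessary condition becomes n_a > 369 × T_a/T_b. With 125 men per arm that still needs placebo exposure about three times filgotinib exposure (369/125 = 2.95).

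**Conclusion.** The formula in SAP 8.1.5.3 is wrong as written. Followed literally, the difference is 100 times too small relative to the group rates, and the interval is too wide by an amount that depends on the counts: about 1.0 to 1.5 times for 0 to 5 events per arm, about 2 times for 10 to 20 filgotinib events, and 3 times or more for common events. With equal exposure it includes zero at every feasible count. The specific intervals rest on the assumed exposure and counts; the ratios rest on equal exposure and on reading the limits per 100 PYE.

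A reader might infer three stronger things that the documents do not support:

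- **The interval is about twice too wide in general.** That figure fits only a middle range of counts.
- **A real excess on filgotinib has been or would be hidden.** The program is not shown, the correct per-arm results appear in the same display, and the mis-scaled difference would be easy to see.
- **Other results are affected.** The semen endpoints use different methods, the per-arm EAIRs and their intervals are on one scale, and the documents attach no decision rule to this descriptive display.

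**What to change.** State that l and u in the MOVER step are the Poisson limits before multiplication by 100, and that the difference, L and U are then multiplied by 100. Equivalently, put the factor of 100 on every n/T term in L and U. Add one worked example and check the program against it; 6 v 0 at 50 PYE per arm should return 12.0 (1.4 to 26.1). Add the two missing methodological sources to Section 10. The cost is one line of SAP wording, two references and a short program check. If the analysis has already been run, confirm which scale the program used and record it in the clinical study report, where SAP Section 1 says that later changes are documented.
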